16.1.1 ADVERSE EVENTS

An overall AE summary presenting the number and percentage of patients within the following categories by treatment group and total will be provided.

- Total number of AEs (each patient might be counted more than once within this item)
- Patients with AEs
- Patients with SAEs
- Patients with AEs with a relationship to IMP as “Possible”, “Probable” and “Certain”
- Patients with severe AEs
- Patients with AEs leading to IMP dose change
- Patient with AEs leading to IMP permanently discontinued

In addition, an analysis using Fisher's exact test to compare the AE incidence between treatment groups will be presented for the following categories:

- Patients with AEs
- Patients with AEs with a relationship to IMP as “Possible”, “Probable” and “Certain”
- Patients with severe AEs

In addition, the following tables will be reported by treatment groups:

- AEs, by SOC, PT and severity
- Related AEs, by SOC, PT and severity

16.1.1.1 Severity

Severity is classified as mild/ moderate/ severe. AEs with a missing severity will be counted in a separate missing category. If a patient reports an AE more than once within that SOC/ PT, the AE with the worst case severity will be used in the corresponding severity summaries.

16.1.1.2 Relationship to Study Medication

Relationship, as indicated by the Investigator, is classed as “Unassessable/Unclassified”, “Conditional/Unclassified”, “Unrelated”, “Unlikely”, “Possible”, “Probable”, and “Certain”. Adverse events with a relationship of “Possible”, “Probable” and “Certain” to IMP will be considered as related to study medication. AEs with a missing relationship to study medication will be counted in a separate missing category. If a patient reports the same AE more than once within that SOC/ PT, the AE with the worst case relationship to study medication will be used in the corresponding relationship summaries.

16.1.2 ADVERSE EVENTS LEADING TO DOSE CHANGE OR DISCONTINUATION OF STUDY MEDICATION

If the action taken for an AE is recorded as “IMP permanently discontinued” on the “Adverse Events” form of the eCRF, it will be considered as an AE leading to permanent discontinuation. If the action taken for an AE is recorded as “IMP dose changed” on the “Adverse Events” form of the eCRF, it will be considered as an AE leading to dose change. These will be summarized by SOC and PT by treatment group and also listed.

Document: Reckitt Benckiser GA1210 Statistical Analysis Plan

Author: [REDACTED]

Version Number:

2.0

Version Date:

29Jul2014

Template No: CS_TP_BS016 – Revision 3

Reference: CS_WI_BS005

Effective Date: 01May2012

Page 19 of 23

16.1.3 SERIOUS ADVERSE EVENTS

SAEs are those events a response of "Yes" for the item "Is the Adverse Event serious?" on the "Adverse Events" form of the eCRF. A summary of SAEs by SOC, PT and severity, as well as a summary of related SAEs by SOC, PT, and severity will be reported by treatment group. Summaries will also be provided for SAEs leading to dose change as well as study discontinuation. These data will also be listed.

16.1.4 ADVERSE EVENTS LEADING TO DEATH

AEs leading to Death are those events with outcome reported as "Fatal" on the "Adverse Events" form of the eCRF. A summary of AEs leading to death by SOC and PT will be prepared. This information will also be listed.

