	Unlikely	Slight, but remote, chance that the AE was caused by the IMP, but the balance of judgment is that it was most likely not due to the IMP.
	Possible	Reasonable suspicion that the AE was caused by the IMP.
	Probable	Most likely that the AE was caused by the IMP.
	Certain	The AE was definitely caused by the IMP.
Is the AE serious?	Results in death Life-threatening Requires or prolongs hospitalisation Results in persistent or significant disability/incapacity Congenital anomaly/birth defect Otherwise considered to be medically significant	See Section 13.1.1.
Date resolved		The date on which the AE ceased to be present.
Outcome	Not recovered/not resolved Recovered/resolved Recovered/resolved with sequelae Recovering/resolving Fatal Unknown	The AE still persists. The AE is resolved. The patient is stabilised, but with sequelae from this AE. The patient is recovering from this AE/this AE is resolving The patient died whilst this AE was ongoing or as a result of it. The outcome of this AE is not known.
Has the patient ever experienced this AE before?	Yes/No	A query confirming whether the patient has a previous medical history of the AE at any time before entering into the study. If the patient has experienced this AE before, brief details should be given under additional information.
Additional information		Additional information regarding the AE.

13.1.4 **Procedure for Reporting Adverse Events**

All AEs that arise after the patient has had IMP administered will be recorded in the patient's CRF. AEs can be reported spontaneously by the patient or in response to non-leading questioning or observation by the Investigator, or be a significant laboratory abnormality.

The Investigator will ask the patient: "Are you experiencing any symptoms or complaints?" at the baseline visit and "Have you had any symptoms or complaints since the last visit?" during the study.

Assessments of the relationship of AEs to IMP must be made by the Investigator (if medically qualified) or by a medically qualified Co-Investigator.

13.1.5 **Procedure for Reporting Serious Adverse Events**

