16.1 ADVERSE EVENTS

Adverse Events (AEs) will be coded using MedDRA version 17.0. For an individual patient, only adverse events commencing after first dose of IMP and no later than last dose of IMP+1day will be included in the AE and serious adverse event (SAE) summaries. AEs that began prior to the first dose of IMP or more than one day after the final dose of IMP will not be included in the analysis. Where an AE start date is partially or completely missing, and it is unclear using partial dates as to whether the AE is treatment-emergent, it will be assumed that it is.

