16.2 DEATH

Only AEs leading to death are recorded for this study, please refer to Section 16.1.4.

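### SAP 16.1.4 labels every AE with outcome 'Fatal' as leading to death, but the protocol's 'Fatal' also covers AEs merely ongoing at death, so a coincidental AE can be tabulated as leading to death

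*SAP*

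**What the plan says.** - **SAP 16.1.4** sets the rule: "AEs leading to Death are those events with outcome reported as" 'Fatal' on the AE form. No second condition is attached. The output follows directly: "A summary of AEs leading to death by SOC and PT will be prepared", together with a listing.
- **Protocol 13.1.3, Table 13-1**, gives the meaning of the outcome 'Fatal': "The patient died whilst this AE was ongoing or as a result of it".
- The same table lists, under the question whether the AE is serious, the criteria "Results in death Life-threatening Requires or prolongs hospitalisation" and others. The first of these is causal. Protocol 13.1.1 uses the same criterion in the SAE definition.
- **SAP 16.2** gives deaths no analysis of their own. It states "Only AEs leading to death are recorded for this study" and refers back to 16.1.4.
- **SAP 10** summarises the reasons for withdrawal by treatment group and overall. Protocol 11.3.2.3 and 11.7.1 include death among those reasons.

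**The concern.** The table's label asserts that the AE led to the death. The code used to fill it does not carry that meaning: the first half of the protocol definition asks only that the AE was still present when the patient died. A headache or constipation ongoing in a patient who dies of something else meets the definition. It could then appear by system organ class and preferred term as an AE leading to death.

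Any such entry would sit in a closely read safety table, and a reader of the table alone would have no means of telling a causal AE from a coincidental one. The protocol already defines an item that makes the distinction, and the SAP rule does not use it.

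**Working it through.** No arithmetic in the plan bears on this. The check is a comparison of definitions, followed by a search of the SAP for anything that narrows the rule.

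**1. What the code means.** Table 13-1 lists six AE outcomes and six definitions in the same order. Matching them in that order, 'Fatal' takes the definition with two alternatives joined by 'or': (a) death while the AE was ongoing, (b) death as a result of the AE. Only (b) is causal.

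**2. What the SAP does with it.** SAP 16.1.4 takes (a) and (b) together and names the whole set AEs leading to death. The label fits (b) only.

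**3. Does anything in the SAP narrow the set?**
- SAP 16.1 restricts AE and SAE summaries to "only adverse events commencing after first dose of IMP and no later than last dose of IMP+1day". This limits onset dates. It does not separate cause from coincidence.
- SAP 16.1.3 identifies SAEs by a 'Yes' to the overall seriousness question and does not mention the individual criteria.
- SAP 16.2 refers back to 16.1.4 and adds no condition.

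Nothing narrows it.

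**4. Must a coincidental AE be coded 'Fatal'?** No. Table 13-1 also offers 'Not recovered/not resolved', defined as the AE still persisting. An AE present at death fits both outcomes. The entry in the table then depends on which one the site picks.

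**5. Size per death (illustration; k is an assumption, not a figure from the documents).** Suppose a patient dies with k AEs ongoing, one of which caused the death, and the site codes all of them 'Fatal':

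- entries shown as leading to death = k
- entries wrongly labelled = k − 1

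| k | Entries shown | Wrongly labelled |
|---|---|---|
| 1 | 1 | 1 − 1 = 0 |
| 2 | 2 | 2 − 1 = 1 |
| 3 | 3 | 3 − 1 = 2 |

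These are upper limits. Each AE coded 'Not recovered/not resolved' instead removes one wrong entry.

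**6. Where deaths can be counted.** The statement in SAP 16.2 is incomplete. The primary reason for withdrawal is a single category per patient and includes death (Protocol 11.7.1), and SAP 10 tabulates it by arm. A death after Visit 3 would not show there, since the patient has completed the study. It could still reach the AE record, because Protocol 13.1.7 has unresolved AEs followed beyond the end of the study. Neither source alone is complete.

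**The case against.** Several points on the other side have force.

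- **The effect is conditional.** It needs a death, a second AE ongoing at that time, and a site that codes that AE 'Fatal'. A reader might infer that unrelated AEs *will* be reported as causes of death. The documents support only that an AE unconnected with the death *can* be tabulated as leading to it. This point stands and limits the finding.
- **Deaths are not uncountable.** A reader might infer from SAP 16.2 that the number of deaths cannot be told apart from the number of AEs. SAP 10 contradicts this: deaths recorded as the withdrawal reason are counted per patient and by arm. What remains is the gap after Visit 3 and the inaccurate statement in 16.2.
- **A 'Fatal' outcome does not make an AE a fatal effect of the drug.** Constipation is a tempting example, but Protocol section 6 links it to high doses of calcium while the minimum dose is studied, and relationship to study medication is assessed separately (SAP 16.1.1.2). That reading is not supported.
- **Other outputs would help expose a wrong entry.** An AE marked 'Fatal' but not serious would be missing from the SAE tables and listings. This is true, but it relies on a reader cross-checking a table whose label is wrong.
- **The present rule is the more inclusive one.** Selecting on 'Results in death' alone would lose a fatal AE where the site left that criterion unticked. This is a fair objection to a bare swap of filters and is why disagreements need a query.
- **The field may not exist separately.** SAP 16.1.3 confirms only a 'Yes' to seriousness on the eCRF. Table 13-1 makes separate collection of the criterion likely but does not settle it.

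None of these removes the mismatch between the label and the code.

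**Conclusion.** The rule in SAP 16.1.4 is wrong as written: it gives a causal label to an outcome code that the protocol defines as causal or coincident in time. The ambiguity begins in Table 13-1, and the SAP label turns it into a statement about cause.

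Materiality is low. Treatment lasts 7 days, the protocol describes the risks as low and excludes severe disease of other major body systems, and the summaries stop at AEs starting one day after the last dose. Few or no entries are expected. Efficacy results are untouched. So are the Fisher tests in SAP 16.1.1, which compare patients with any AE, related AEs and severe AEs.

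The conclusion rests on reading the flattened outcome list in Table 13-1 in order, and on there being no narrower instruction in the eCRF completion material, which is not among the documents.

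**What to change.** 1. **SAP 16.1.4.** Define AEs leading to death as those with the seriousness criterion 'Results in death' (Table 13-1). First confirm in the annotated eCRF that the criterion is a separate field. Query every AE where this criterion and outcome 'Fatal' disagree, so that no fatal AE is lost through an unticked box.
2. **If the field is not available,** or the database can no longer be queried, keep the filter, retitle the table 'AEs with outcome Fatal' and footnote the protocol definition.
3. **SAP 16.2.** Replace the statement that only AEs leading to death are recorded with a count of patients who died, by arm, each patient counted once. Take it from the AE records ('Fatal' or 'Results in death') and reconcile it with withdrawal reason 'death' in SAP 10, so that a death after Visit 3 recorded on the AE form is also captured. An AE coded 'Fatal' under either half of the definition still identifies a patient who died, so the code is sound for this purpose.
4. **Listing.** Show other AEs ongoing at death in the listing only.

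Cost: a few SAP sentences, one filter or footnote in the table program, one count by arm, and queries only for discordant AEs, of which few or none are expected.

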16.2 DEATH

Only AEs leading to death are recorded for this study, please refer to Section 16.1.4.

16.3 LABORATORY EVALUATIONS

Clinical assessments on hematology and clinical chemistry are to be measured at Visit 1 and Visit 3 or Early Termination Visit. A list of laboratory assessments to be included in the outputs is provided in appendix 1. Local laboratories will be used for the assessment of hematology and clinical chemistry data and these data will be converted to the International System (SI) of units by Data Management Team using standard conversion factors. Quantitative laboratory measurements reported as "< X", i.e. below the lower limit of quantification (BLQ), or "> X", i.e. above the upper limit of quantification (ULQ), will be converted to X for the purpose of quantitative summaries, but will be presented as recorded, i.e. as "< X" or "> X" in the listings.

At each visit, summary statistics for the absolute laboratory value and the changes from baseline will be presented by treatment group. The significance of within-treatment changes from baseline will be assessed using the Wilcoxon Signed-Rank Test. The significance of between treatment changes from baseline will be assessed using the Wilcoxon Rank-Sum Test. Statistical testing will be performed at last visit.

Each pre-study baseline laboratory value will be categorised as low, normal, or high based on the reference range of the local laboratories:

- Low: Below the lower limit of the laboratory reference range.
- Normal: Within the laboratory reference range (upper and lower limit included).
- High: Above the upper limit of the laboratory reference range.

Each post-baseline value will be classified in a similar manner, producing a 3 x 3 table for each treatment group at each post-baseline visit. Scores of "1" will be assigned to low values, "2" to normal values, and "3" to high values. Using these scores, shifts from baseline will also be assigned a score. For example, a laboratory value that shifts from low to high will be assigned a score of 2, whilst a laboratory value that remains at a low value will be assigned a score of 0. Shifts between these categories between baseline and subsequent timepoints (Visit 3

Document: Reckitt Benckiser GA1210 Statistical Analysis Plan

Author:

Version Number:

2.0

Version Date:

29Jul2014

Template No: CS_TP_BS016 – Revision 3

Effective Date: 01May2012

Reference: CS_WI_BS005

Page 20 of 23

or Early Termination Visit) will be compared using the Wilcoxon Signed-Rank test within each treatment group. Statistical testing will be performed at last visit.

In addition to the high and low quantitative laboratory assignments (as identified by means of the laboratory reference ranges), clinically significant quantitative laboratory assessments will be identified by investigator and the result will be recorded in the eCRF. The number and percentage of patients with abnormal or clinically significant results will be tabulated by treatment groups by visit. The results will also be listed.

Women of child-bearing potential will undergo urine pregnancy testing (positive or negative). The results will be listed.

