7.5. COMMON CALCULATIONS

For quantitative measurements, change from baseline will be calculated as:

- Test Value at Visit X – Baseline Value

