8. STATISTICAL CONSIDERATIONS

8.1. MULTICENTER STUDIES

This study will be conducted at multiple hospital sites. Allocation to treatment arms is stratified by centre.

Centre pooling will be carried out across all centres for use in statistical summaries for this study. Centre will be

Document:	Reckitt Benckiser GA1210 Statistical Analysis Plan		
Author:	[REDACTED]	Version Number:	2.0

Version Date: 29Jul2014

Template No: CS_TP_BS016 – Revision 3

Reference: CS_WI_BS005

Effective Date: 01May2012

Page 11 of 23

included in the statistical models to adjust for centre effect. Treatment by centre interaction may also be explored using additional analyses. Refer to Section 15 for more details.

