9. OUTPUT PRESENTATIONS

The templates provided with this SAP describe the presentations for this study and therefore the format and content of the summary tables, figures and listings to be provided by Quintiles Biostatistics.

Continuous variables will be summarized using descriptive statistics, i.e., number of subjects (n), mean, median, standard deviation, minimum and maximum.

Qualitative variables will be summarized by counts and percentages. Unless otherwise stated, the calculation of proportions will be based on the sample size of the population of interest.

Document: Reckitt Benckiser GA1210 Statistical Analysis Plan

Author: [REDACTED]

Version Number:

2.0

Version Date:

29Jul2014

Template No: CS_TP_BS016 – Revision 3

Reference: CS_WI_BS005

Effective Date: 01May2012

Page 12 of 23

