16.4 VITAL SIGNS

Vital signs including systolic/diastolic blood pressure (mmHg) and heart rate (beats/min) will be conducted at Visit 1 and Visit 3 or early termination visit.

At each visit, summary statistics for the absolute vital sign value and the changes from baseline will be presented by treatment group. The significance of within-treatment changes from baseline will be assessed at the last visit, using the Wilcoxon Signed-Rank Test. The significance of between treatment changes from baseline will be assessed at the last visit using the Wilcoxon Rank-Sum Test.

A complete listing on all patients' vital sign result will be presented.

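### The between-arm test of laboratory and vital-sign changes is valid, but it has no baseline covariate or centre stratum and gives a p-value without an estimated difference or confidence interval

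*SAP*

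**What the plan says.** For laboratory values SAP 16.3 specifies: "The significance of between treatment changes from baseline will be assessed using the Wilcoxon Rank-Sum Test". For vital signs SAP 16.4 has: "The significance of between treatment changes from baseline will be assessed at the last visit using the Wilcoxon Rank-Sum Test". Protocol 14.5.2 and 14.5.3 prespecify the same tests. None of the four sections names a covariate or a stratum. The tested variable is defined in SAP 7.5 as "Test Value at Visit X – Baseline Value".

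On reporting, SAP 16.3 says "summary statistics for the absolute laboratory value and the changes from baseline will be presented by treatment group", and SAP 9 sets the content: "Continuous variables will be summarized using descriptive statistics, i.e., number of subjects (n), mean, median, standard deviation, minimum and maximum". No between-arm difference or interval is listed for any of the 15 analytes in SAP Appendix 1 or for the three vital signs (systolic and diastolic pressure, heart rate). Low/normal/high shifts are tested only within each arm, and abnormal or clinically significant results are tabulated by arm without a test.

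On centre, SAP 16.3 says "Local laboratories will be used for the assessment of hematology and clinical chemistry data", with conversion to SI units. SAP 8.1 says "Allocation to treatment arms is stratified by centre", and that centre will be "included in the statistical models to adjust for centre effect", pointing to Section 15 for detail. In Section 15, the RDQ dimension scores get a mixed model with baseline covariate, random centre and least-squares means with 95% CI (15.1.3). The OTE responses and RDQ items get a rank-sum test stratified by centre (15.2.3).

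**The concern.** The rank-sum test is the only between-arm inference planned for laboratory values and vital signs, and it is the one comparison of measured changes in the SAP that uses neither baseline adjustment nor centre. Protocol section 6 lists raised plasma sodium and, at high doses, hypercalcaemia among the possible reactions to the active ingredients. A reader of the report will want to know how large a shift in sodium, calcium or blood pressure the data exclude. A p-value does not answer that, and a non-significant one can be mistaken for evidence of no effect. Precision is also given up although the Visit 1 value and the centre are already on file.

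**Working it through.** **The plan's own figure.** No power or precision is stated for the safety tests. The only sizing figure is 1054 evaluable patients (Protocol 14.1: effect size 0.2, two-sided 5%, 90% power). The normal approximation gives 2 × (1.960 + 1.2816)² / 0.2² = 525.4, so 526 per arm and 1052 in total. The exact two-sample t-test gives 526.33, so 527 per arm and 1054 in total. The figure reproduces and fixes the scale of the trial. Below, 550 per arm is used (1100 randomised).

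**Assumptions.** The documents give neither the Visit 1 to Visit 3 correlation (r) nor the share of variance in change that lies between centres (ICC). Both are varied. Visit SDs are set equal to 1, so shifts are in SD units.

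**Formulas (normal data).**
- Variance of the raw change: 2(1 − r).
- Variance after baseline adjustment: 1 − r². The ratio to the raw change is (1 + r)/2.
- Efficiency of the rank-sum test against the t-test: 0.955.
- Relative efficiency of the planned test with no centre effect: 0.955 × (1 + r)/2.
- Shift detectable with 90% power: 3.2415 × √(2V/550), where V is the relevant variance (divided by 0.955 for the rank-sum test).

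**Worked case, r = 0.5.** Adjusted: 3.2415 × √(2 × 0.75/550) = 0.169 SD. Planned: 3.2415 × √(2 × 1/(0.955 × 550)) = 0.200 SD. At a true shift of 0.169 SD the planned test has standardised effect 0.1693/0.0617 = 2.743. Its power is Φ(2.743 − 1.960) = 78%, against 90%.

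| r | Relative efficiency | Detectable shift, planned | Detectable shift, adjusted | Planned power when adjusted model has 90% (ICC 0) | Same, ICC 0.10 |
|---|---|---|---|---|---|
| 0.5 | 0.716 | 0.200 | 0.169 | 78% | 74% |
| 0.6 | 0.764 | 0.179 | 0.156 | 81% | 77% |
| 0.7 | 0.812 | 0.155 | 0.140 | 83% | 79% |
| 0.8 | 0.859 | 0.127 | 0.117 | 85% | 81% |

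The relative efficiency and detectable shifts are for ICC 0. The loss without a centre effect therefore runs from about 12 points (r = 0.5) to 5 points (r = 0.8). Not all of it comes from the missing covariate. At r = 0.5 an unadjusted t-test on change would have Φ(0.1693/0.0603 − 1.960) = 80%, so about 2 of the 12 points are the price of ranking normal data.

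**Simulation of the same comparison** (1500 runs, 1100 patients, 37 centres, laboratory offsets common to both visits, centre fitted as fixed). Planned against adjusted power was 78% vs 90% (r = 0.5, ICC 0) and 83% vs 89% (r = 0.8, ICC 0.10). With no true shift at r = 0.5, the planned test rejected 4.5% (ICC 0) and 3.9% (ICC 0.10). Monte Carlo error at 5% is √(0.05 × 0.95/1500) = 0.6 points.

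**Centre.** A second simulation (30 equal centres, r = 0.6, shift 0.15 SD) compared the planned test, the centre-stratified rank test and the baseline- and centre-adjusted model:
- No centre-specific change: 77%, 76%, 87%.
- Centre-specific change of SD 0.3 (ICC 0.09/(0.09 + 0.80) = 0.10): 75%, 77%, 87%.
- SD 0.5 (ICC 0.25/(0.25 + 0.80) = 0.24): 69%, 77%, 87%.
- SD 0.5, no true shift: 3.1%, 6.0%, 5.3% rejections.

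Stratifying gains nothing when changes do not vary by centre and restores power when they do.

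**Departure from normality.** With 550 per arm, no centre effect and t-distributed visit errors on 3 degrees of freedom, the planned test beat the adjusted model: 93% vs 87% (r = 0.6, shift 0.15 SD) and 95% vs 86% (r = 0.8, shift 0.11 SD). A repeat simulation gave 94% vs 90% and 94% vs 84%. For lognormal data left on the raw scale the two were close: 77% vs 81% and 78% vs 77%.

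**The case against.** The case for leaving the plan alone is substantial, and most of it stands.

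- A reader might infer that baseline is ignored. It is not: the test is run on visit value minus baseline. Only covariate adjustment is absent.
- A reader might infer that differences between local laboratories contaminate the comparison. A constant offset cancels in the change if one laboratory handles both visits, and Protocol 13.4 has samples analysed by the hospital laboratory at each site. Only drift or scale differences remain. The documents give no evidence of drift over a participation of at most 17 days, and centre-stratified allocation keeps it from biasing the comparison.
- A reader might take SAP 8.1 as contradicted. It speaks of models and refers to Section 15, which is efficacy, so it does not bind a rank test in Section 16.
- A reader might conclude that sensitivity is lost. It is reduced, under normality, by a moderate amount. The planned test still has 90% power for shifts of about 0.13 to 0.20 SD over r of 0.8 to 0.5. Rank methods also suit outliers and values reset to a quantification limit.
- An approximate unadjusted interval can be built from the planned tables: the difference in mean change, with standard error √(SD₁²/n₁ + SD₂²/n₂).
- The sodium and calcium risks are tied in the protocol to restricted-salt patients and to high doses. Exclusion criteria 12 and 14 remove known hypercalcaemia and patients needing a low-sodium diet, and SAP 3.3 defines the safety objective by adverse events.

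These points rule out any claim of bias or invalidity, and any case for dropping the rank test. They do not supply a planned, baseline-adjusted estimate with its interval, nor explain why the safety rank tests omit the centre stratum that the efficacy rank tests have.

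**Conclusion.** The point holds as a minor one. The planned comparison is valid, but it gives only a p-value and leaves baseline covariate and centre unused. The missing difference and interval follow from the text and need no assumption. The power cost does need assumptions: about 5 to 12 points against a baseline-adjusted model with 90% power, for normal data, equal visit SDs, r from 0.8 to 0.5 and no centre effect. If changes do differ by centre, the planned test becomes slightly conservative (3.9% at ICC 0.10 in one simulation, 3.1% at drift SD 0.5 in another) and the gap widens. With heavy tails the ordering reverses, so replacing the rank test outright would be a trade-off, while adding an estimate beside it is not. Efficacy conclusions and the adverse-event safety measure are unaffected.

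**What to change.** In SAP 16.3 and 16.4:

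1. Keep the Wilcoxon test for the between-arm comparison but stratify it by centre, with the SAP 15.2.3 method.
2. For each parameter, add the between-arm difference in change, adjusted for the baseline value with centre as a random effect, and its 95% CI, from the SAP 15.1.3 code. Name in advance the skewed analytes (ALT and AST, for example) to be analysed on the log scale.
3. State in the SAP that this departs from Protocol 14.5.2 and 14.5.3. Protocol 14 provides for such deviations to be recorded there.

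No new data are needed. The cost is a choice of scale for skewed analytes and a few more outputs. The change form dated 1 September 2014 at the end of the SAP shows that unblinded output had by then been reviewed. Estimates added after that point should be labelled as post hoc and shown beside the planned test.
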